7.1.5 Follow up for Subjects with a Suspicion for Myocarditis and/or Pericarditis

In the event that a subject develops symptoms which in the judgement of the investigator, is consistent with a case of suspected myocarditis and/or pericarditis within 4 weeks from vaccination, the site will conduct an unscheduled illness visit. Additionally, a serum sample will be obtained and stored for potential biomarker testing at a central laboratory. The site will coordinate an appropriate diagnostic workup to make a determination of probable or confirmed myocarditis and/or pericarditis which may include, but is not limited to, an ECG, cardiac troponin testing (T or I) and referral to a cardiologist (directly, or through the emergency department or primary care clinic). The suspected myocarditis and/or pericarditis case should be reported to the DMID Medical Monitor within 24 hours of site awareness.

The definitions below are intended to serve as a guide to help in the reporting of suspected cases of myocarditis and/or pericarditis; however, the diagnosis of suspected cases is left to the investigator's clinical judgement.

7.1.5.1 Probable Case of Acute Myocarditis

Presence of ≥ 1 new or worsening of the following clinical symptoms:

- Chest pain/pressure/discomfort
- Dyspnea/shortness of breath/pain with breathing
- Palpitations
- Syncope

AND

Presence of ≥ 1 new finding of the following:

- Troponin level above upper limit of normal (any type of troponin)
- Abnormal electrocardiogram (ECG or EKG) or rhythm monitoring findings consistent with myocarditis which includes at least one of the following:
 - ST segment or T-wave abnormalities
 - Paroxysmal or sustained atrial, supraventricular, or ventricular arrhythmias
 - AV nodal conduction delays or intraventricular conduction defects
- Abnormal cardiac function or wall motion abnormalities on echocardiogram
- Cardiac magnetic resonance imaging (cMRI) finding consistent with myocarditis⁵⁵

AND

- No other identifiable cause of the symptoms and findings

7.1.5.2 Confirmed Case of Acute Myocarditis

Meets the case definition for a probable case

AND

- Histopathologic confirmation of myocarditis (using Dallas criteria)⁵⁶ OR
- cMRI findings consistent with myocarditis in the presence of troponin level above upper limit of normal (any type of troponin)

AND

- No other identifiable cause of the symptoms and findings

7.1.5.3 Acute Pericarditis Case Definition

Presence of ≥ 2 new or worsening of the following clinical features⁵⁷:

- Acute chest pain (Typically described as pain made worse by lying down, deep inspiration, or cough; and relieved by sitting up or leaning forward, although other types of chest pain may occur)
- Pericardial rub on examination
- New ST-elevation or PR-depression on EKG
- New or worsening pericardial effusion on echocardiogram or magnetic resonance imaging

7.1.5.4 Myopericarditis Case Definition

Participants who meet criteria for both myocarditis and pericarditis may be described under myopericarditis.

7.2 Subject Withdrawal from the Study and Replacement

Subjects are free to withdraw from participation in the study at any time upon request, without any consequence.

A study subject will be discontinued from participation in the study if any of the following reasons occur prior to initial dosing:

- Request by the subject to terminate participation.
- Initial vaccine is not administered.

A subject may be removed from the study for the following reasons post initial dosing; however, whenever possible the subject should be followed for safety and immunogenicity evaluations per protocol:

- Subject becomes pregnant before receiving the additional dose of vaccine.
- Study non-compliance to protocol requirements that in the opinion of the participating site PI or appropriate sub-investigator poses an increased risk or compromises the validity of the data.
- Lost to follow-up.
- If the subject met an exclusion criterion for participation in the study (either newly developed or not previously recognized) that precludes further study participation.
- Request of primary care provider, the IRB, FDA, or NIAID.
- Medical disease or condition, or new clinical finding(s) for which continued participation, in the opinion of the participating site PI or appropriate sub-investigator might compromise the safety of the subject, interferes with the subject's successful completion of this study, or interferes with the evaluation of responses.
- If any AE or situation occurs such that continued participation in the study would not be in the best interest of the subject.

- Any SAE judged to be related to vaccine.

If the subject agrees, every attempt will be made to follow all AEs through resolution or stabilization.

Subjects who withdraw, or are withdrawn from this study, or are lost to follow-up after signing the informed consent form (ICF) and administration of the study product will not be replaced.

Subjects who withdraw, or are withdrawn from this study, or are lost to follow-up after signing the ICF but before administration of the first study product may be replaced.

The reason for subject discontinuation or withdrawal from the study will be recorded on the appropriate DCF.

7.3 Lost to Follow-Up

A subject will be considered lost to follow-up if he or she fails to appear for a follow-up assessment. Extensive effort (i.e., generally three documented contact attempts via telephone calls, e-mail, etc., made on separate occasions) will be made to locate or recall the subject, or at least to determine the subject's health status. These efforts will be documented in the subject's study file.

8. STUDY ASSESSMENTS AND PROCEDURES

8.1 Screening and Immunogenicity Assessments

8.1.1 Screening or Enrollment/Baseline Procedures

There is a small amount of risk to subjects who report that they are in stable state of health but have an unknown health problem at the time of the enrollment/baseline visit. Screening assessments can occur up to 28 days before or at the subject's first vaccination visit (Day 1). At the screening (optional) or enrollment visit, and prior to any other study-related activities, the participating site PI or appropriate designee will provide the subject with detailed study information and will obtain written informed consent.

Some or all of the following assessments are performed during the screening (optional) or enrollment visit to determine eligibility requirements as specified in the inclusion and exclusion criteria:

- Obtain a complete medical history.
- Demographic information.
- Review pre-study medications at screening and record on the appropriate DCF (refer to [Section 6.5](#)). Review all licensed/approved and any experimental vaccines (the review of licensed/approved vaccines other than COVID-19 vaccines is limited to 28 days prior to screening/enrollment).
- Review any participation in investigational trials in the last 28 days.
- Measure vital signs (HR, BP, and oral temperature), and height and weight for determination of BMI.
- Targeted physical examination. A targeted exam is one that is targeted to assess any symptoms or medical conditions. The site PI (or designee) determines what exam is needed. An individual with no symptoms and no relevant medical history (or a medical history that is unlikely to reveal anything on medical exam) may not need any physical exam.
- Urine pregnancy test (in subjects of childbearing potential). If urine pregnancy is done at separate screening visit, repeat urine pregnancy test will be done within 24 hours of study vaccine administration.
- Review inclusion and exclusion criteria.

The screening process can be suspended prior to complete assessment at any time if exclusions are identified by the study team.

Study subjects who qualify for inclusion will be contacted and scheduled for enrollment and first vaccination within the window for enrollment unless the screening and vaccination are scheduled on the same day.

If a physiologic parameter, e.g., vital signs, is abnormal and potentially clinically significant, then the measurement may be repeated if, in the judgment of the participating site PI or appropriate designee, the abnormality is the result of an acute, short-term, rapidly reversible condition (e.g.,

stress, anxiety or “white coat syndrome”) or other source of error. A physiologic parameter may also be repeated if there is a technical problem with the measurement caused by malfunctioning, or an inappropriate measuring device (i.e., inappropriate-sized BP cuff).

A subject may be re-screened if there is a transient disease status (e.g., subject complained of a “cold or fever” and met a temporary delaying enrollment criterion of acute illness or fever), or if a protocol eligibility criterion that is not met at the initial time of screening, will be met by rescreening at a later date (e.g., a medication taken within exclusionary window at the time of first screening that would not be within exclusionary window at a later rescreen).

Subjects will be provided the results of abnormal clinical findings necessitating follow-up at the discretion of the participating site PI or appropriate designee. Research laboratory results will not be provided to the subject with the exception of urine pregnancy test and SARS-CoV-2 local testing results.

The screening and first vaccination procedures both can be conducted at the enrollment visit.

8.1.2 Immunogenicity Evaluations

Humoral Immunogenicity Assays:

The following humoral immunogenicity assays may be performed:

- IgG ELISA or Multiplex MSD antibody binding assays to SARS-CoV-2 proteins (may include nucleocapsid protein, and multiple variant Receptor binding domains and variant spike proteins).
- Neutralization assays using SARS-CoV-2 variant specific S-pseudotyped viruses.
- Neutralization assay using different strains of live SARS-CoV-2.
- Characterization of antigen-specific antibody by a) subclass, b) isotype, c) ability to interact with Fc receptors, d) innate immune receptors, e) lectin-like molecules and f) lectins at different times post-vaccination.
- Functional Fc effector assays which may include quantification of antigen specific antibody-mediated NK cell activation (ADCC-NK) levels, antibody-dependent cellular phagocytosis (ADCP) activity, Antibody-dependent complement deposition (ADCD) and/or Antibody-dependent neutrophil activation/phagocytosis activity.

Preparation of blood samples and shipping instructions for serological immunogenicity assays are outlined in the protocol-specific MOP. Inability (e.g., failure of venipuncture) to collect all baseline samples on Day 1 will not exclude the subject from further participation in this study as long as a minimum of baseline serum for serological immunogenicity assays is collected (refer to protocol-specific MOP).

Cellular Immunology Assays:

This trial may also investigate innate, B and T cell immune responses using multiparametric flow cytometry. Refer to the protocol-specific immune monitoring plan for details.

Preparation of blood samples and shipping instructions for cellular immunology assays are outlined in the protocol-specific MOP.

The volume of venous blood to be collected for immunogenicity evaluations is presented in [Table 2](#) and [Table 3](#).

8.1.3 Samples for Suspected SARS-CoV-2 infection

In the event that a subject develops symptoms compatible with COVID-19, the site will follow with an unscheduled Illness Visit in person or by phone (with the participant self-collecting the swab). If a participant is asymptomatic but tests positive for COVID-19 outside the study, the site will follow the same procedure. Wide discretion is given to sites for the assessment of COVID-19 illness. Guidance can be found at the CDC website (2021 Case Definition):

[Coronavirus Disease 2019 \(COVID-19\) 2021 Case Definition | CDC](#)

The following intervention will be performed in the event of an illness visit:

- Nasal swabs for PCR and sequencing

One to two nasal swabs will be obtained for the purposes of 1) conducting qualitative analysis to assess for the presence of SARS-CoV-2 virus, and 2) conducting PCR quantitation/sequencing in the event that nasal swab #1 is positive for SARS-CoV-2. If a test outside the study was found to be positive only one swab is needed for sequencing.

The first nasal swab, as applicable, will be processed at the local level with results informing the disposition of the second nasal swab. The sites will freeze and store the second swab (refer to MOP for labeling, storage, and shipping instructions) for potential shipment to the central repository for testing.

8.1.4 Samples for Genetic/Genomic Analysis

8.1.4.1 Genetic/Genomic Analysis

DNA obtained from B-cells may be sequenced to identify B cell receptors and monoclonal antibodies. The DNA data may be used to synthesize antigen-specific antibodies to characterize antibody binding. Secondary research samples may also be used for other genomic analysis, including, but not limited to, single nucleotide polymorphisms (SNP) arrays, human leukocyte antigen (HLA) typing, transcriptomic analysis, evaluation of the immune response to the vaccine, and/or evaluation of any AE from the vaccine.

8.1.4.2 Genetic Privacy and Confidentiality

Any genetic data generated will be kept private. Informed consent permitting data sharing will be part of the consent process. Subjects will be informed that the evolution of genomic technology and analytical methods raises the risk of re-identification, even when specimens are de-identified. No data that may identify specific subjects will be kept with the genetic data.

8.1.4.3 Management of Results

All genetic testing in this protocol will be performed for research purposes only and is not performed in a Clinical Laboratory Improvement Amendments (CLIA) certified laboratory. Therefore, results will not be shared with the subjects.

8.1.5 SARS-CoV-2 infection

Confirmed SARS-CoV-2 infection at any time during the study, defined as a positive RT-PCR test performed by the site or using a non-site testing method (RT-PCR or antigen test), will be documented. While this event would occur on study, it is not a typical AE and therefore captured as an exploratory efficacy assessment.

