
 To assess, in at least a subset of samples, the functional potential of SARS-CoV-2 specific antibodies to mediate Fc-effector functions across candidate SARS-CoV-2 variant vaccines. 	
 Characterization of antigen-specific antibody by a) subclass, b) isotype, c) ability to interact with Fc receptors, d) innate immune receptors, e) lectin-like molecules and f) lectins at different times post-vaccination. Functional Fc effector assessments which may include quantification of antigen specific antibody-mediated NK cell activation (ADCC-NK) levels, antibody-dependent cellular phagocytosis (ADCP) levels, antibody-dependent complement deposition (ADCD) and/or antibody-dependent neutrophil activation/phagocytosis levels at different times post-vaccination.

 To evaluate breakthrough SARS-CoV-2 infection by sequencing strains for variant spike lineage and assessing anti- nucleocapsid serology. 	
 Sequence analysis on breakthrough NAAT-confirmed SARS-CoV-2 strains at any time post-vaccination Anti- nucleocapsid immunoassay at different times post-vaccination.

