8.3 Adverse Events and Serious Adverse Events

8.3.1 Definition of Adverse Event (AE)

AE means any untoward medical occurrence associated with the use of an intervention in humans, whether or not considered intervention-related [21 CFR 312.32 (a)]. An AE can therefore be any unfavorable and unintended sign, symptom or disease temporally associated with the use of medicinal (investigational) product.

Any medical condition that is present at the time that the subject is screened will be considered as baseline and not reported as an AE. However, if the severity of any pre-existing medical condition increases, it should be recorded as an AE.

AEs can be further divided into solicited AEs and unsolicited AEs. Solicited AEs are those that are described in the package insert as local or systemic reactogenicity occurring in the first 7 days after vaccination. Unsolicited AEs are those events that the subject reports occurring without being queried about the specific event.

AEs will be assessed for severity and relationship to study intervention ([Section 8.3.4](#)). Reporting of all AEs, solicited and unsolicited, will occur during the period from study product administration on Day 1 through 28 days after each vaccination. After 28 days post last vaccination through the end of study, only SAEs, Protocol Specified AESIs, MAAEs, NOCMCs, and AEs leading to withdrawal from the study will be reported.

All AEs, solicited and unsolicited, will be captured on the appropriate DCF. Solicited AEs will be regarded as related to the study product and will not require separate entry into the AE log. Information to be collected for unsolicited AEs includes event description, date of onset, assessment of severity, relationship to study product and alternate etiology (assessed only by those with the training and authority to make a diagnosis and listed on the Form FDA 1572 as the participating site PI or appropriate sub-investigator), date of resolution, seriousness, and outcome. AEs occurring during the study-collection and reporting period will be documented appropriately regardless of relationship.

AEs will be followed to resolution or stabilization.

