8.3.2 Definition of Serious Adverse Event (SAE)

An SAE is defined in 21 CFR 312.32 as follows: “An AE or suspected adverse reaction is considered serious if, in the view of either the participating site PI or appropriate sub-investigator or the sponsor, it results in any of the following outcomes:

- Death,
- a life-threatening AE,
- inpatient hospitalization or prolongation of existing hospitalization,
- a persistent or significant incapacity or substantial disruption of the ability to conduct normal life functions,
- or a congenital anomaly/birth defect.

Important medical events that may not result in death, be life-threatening, or require hospitalization may be considered serious when, based upon appropriate medical judgment, they may jeopardize the patient or subject and may require medical or surgical intervention to prevent one of the outcomes listed in this definition. Examples of such medical events include allergic bronchospasm requiring intensive treatment in an emergency room or at home, blood dyscrasias or convulsions that do not result in inpatient hospitalization, or the development of drug dependency or drug abuse.”

“Life-threatening” refers to an AE that at occurrence represents an immediate risk of death to a subject. An event that may cause death if it occurs in a more severe form is not considered life-threatening. Similarly, a hospital admission for an elective procedure is not considered an SAE.

All SAEs, as with any AE, will be assessed for severity and relationship to study intervention.

All SAEs will be recorded on the appropriate SAE DCF.

All SAEs will be followed through resolution or stabilization by a study clinician, licensed to make medical diagnoses and listed on the Form FDA 1572 as the participating site PI or appropriate sub-investigator.

All SAEs will be reviewed and evaluated by DMID and will be sent to the DSMB (for periodic review unless related) and IRB/IEC as needed.

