
12. APPENDIX A: Adverse Events of Special Interest (AESIs) Terms

Investigators should report all events which fall into the following categories as an AESI per the reporting processes specified in the protocol. The following AESIs are medical concepts that may be related to COVID-19 or are of interest in COVID-19 vaccine safety surveillance. Even if the events below occur in the setting of a SARS-CoV-2 infection, the event should still be reported as an AESI if it is one of the medical concepts below. SARS-CoV-2 infection will not be reported using the AESI reporting system. For documentation and medical assessment purposes all AESIs will also be reported on an SAE form and must be submitted immediately (within 24 hours of site awareness) to the DMID Pharmacovigilance Group; however, when applicable, the narrative will indicate that the AESI did not meet SAE criteria.

Medical Concept	Additional Notes
Anosmia, Ageusia	
 • New onset COVID associated or idiopathic events without other etiology excluding congenital etiologies or trauma
Subacute thyroiditis	
 • Including but not limited to events of: atrophic thyroiditis, autoimmune thyroiditis, immune-mediated thyroiditis, silent thyroiditis, thyrotoxicosis and thyroiditis
Acute pancreatitis	
 • Including but not limited to events of: autoimmune pancreatitis, immune-mediated pancreatitis, ischemic pancreatitis, edematous pancreatitis, pancreatitis, acute pancreatitis, hemorrhagic pancreatitis, necrotizing pancreatitis, viral pancreatitis, and subacute pancreatitis • Excluding known etiologic causes of pancreatitis (alcohol, gallstones, trauma, recent invasive procedures)
Appendicitis	
 • Include any event of appendicitis
Rhabdomyolysis	
 • New onset rhabdomyolysis without known etiology such as excessive exercise or trauma
Acute respiratory distress syndrome (ARDS)	
 • Including but not limited to new events of ARDS and respiratory failure

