Medium sized and/or small vessels vasculitis	
Including but not limited to:
 
 Anti-neutrophil cytoplasmic antibody (ANCA) positive vasculitis (type unspecified) Behcet's syndrome Buerger's disease (thromboangiitis obliterans) Churg–Strauss syndrome (allergic granulomatous angiitis) Erythema induratum (also known as nodular vasculitis) Henoch-Schonlein purpura (also known as IgA vasculitis) Microscopic polyangiitis Necrotizing vasculitis Polyarteritis nodosa Single organ cutaneous vasculitis, including leukocytoclastic vasculitis, hypersensitivity vasculitis and acute hemorrhagic edema of infancy (AHEI) Wegener's granulomatosis
Other (including multisystemic)	

Medical Concept	Additional Notes
Anti-synthetase syndrome	
Capillary leak syndrome	
 Frequently used related terms include : “systemic capillary leak syndrome (SCLS)” or “Clarkson’s Syndrome”
Goodpasture syndrome	
 Frequently used related terms include : “pulmonary renal syndrome” and “anti-Glomerular Basement Membrane disease (anti-GBM disease)”
Immune-mediated enhancement of disease	
 Includes vaccine associated enhanced disease (VAED and VAERD). Frequently used related terms include “vaccine-mediated enhanced disease (VMED)”, “enhanced respiratory disease (ERD)”, “vaccine-induced enhancement of infection”, “disease enhancement”, “immune enhancement”, and “antibody-dependent enhancement (ADE)”
Immunoglobulin G4 related disease	
Langerhans' cell histiocytosis	
Multisystem inflammatory syndromes	
Including but not limited to:
 
 Kawasaki’s disease Multisystem inflammatory syndrome in adults (MIS-A) Multisystem inflammatory syndrome in children (MIS-C)
Overlap syndrome	
Raynaud's phenomenon	
Sarcoidosis	
 Includes Loefgren syndrome
Susac's syndrome

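### Section 8.1.5 and the general AE/SAE rules classify a serious COVID-19 case differently, and the protocol does not say which governs

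*Protocol*

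**What the plan says.** Four parts of the protocol bear on how a COVID-19 illness during the study is classified.

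- **Section 8.1.5** defines the event by a test result: "Confirmed SARS-CoV-2 infection at any time during the study, defined as a positive RT-PCR test performed by the site", or a positive PCR or antigen test done elsewhere. It says the event will be documented and then classifies it: "While this event would occur on study, it is not a typical AE and therefore captured as an exploratory efficacy assessment". It sets no severity limit and makes no exception for cases that lead to admission or death.
- **Section 8.3.1** gives the general definition: "AE means any untoward medical occurrence associated with the use of an intervention in humans, whether or not considered intervention-related". It makes no exception for COVID-19.
- **Sections 8.3.2 and 8.3.7.1** build on that definition. The SAE definition opens with "An AE or suspected adverse reaction is considered serious if" and lists death and inpatient admission among the outcomes. The 24-hour reporting duty likewise applies to an AE that meets an SAE criterion.
- **Appendix A (Section 12)** says "SARS-CoV-2 infection will not be reported using the AESI reporting system". It also says that a listed medical concept occurring during an infection is still an AESI, to be sent on an SAE form within 24 hours.

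The exploratory endpoint for infection in Table 4 (Section 3) is "Sequence analysis on breakthrough NAAT-confirmed SARS-CoV-2 strains at any time post-vaccination" together with anti-nucleocapsid serology. Neither measures severity, admission or death.

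**The concern.** Section 8.1.5 is the only rule written specifically for COVID-19, and it reads as a classification: infection is not typical of an AE, so it goes to an exploratory assessment instead. The general rules in 8.3 point the other way for any illness that leads to admission or death. Site staff holding both sections could reasonably choose either.

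SAEs up to 12 months after the last dose are part of the secondary objective. The DSMB receives cumulative AE reports by arm (9.4.6.1). Safety summaries by arm may be published while the study is running (9.4.6). An SAE judged related to vaccine is a halting criterion (7.1.1). If the classification depends on which section a site follows, these outputs rest on inconsistent counting. The study allows up to 30 sites and aims for about 45% of participants aged 65 or over in stages 1 to 3.

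**Working it through.** No figure is at issue, so the check is to follow one case through every rule that might capture it. The case is an illustration: a participant with PCR-confirmed COVID-19, admitted for longer than 24 hours, more than 28 days after the last dose, with no event on the Appendix A list.

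1. **Infection rule (8.1.5).** The positive test meets the definition. The event is documented as an exploratory efficacy assessment. Nothing further is said about seriousness.
2. **Unsolicited AE (8.3.1, 8.3.5).** Collection of general AEs ends 28 days after the last vaccination. After that, only SAEs, AESIs, medically attended AEs (MAAEs), new chronic conditions and AEs leading to withdrawal are reported. For late infections, SAE status therefore largely decides whether the illness enters the safety data.
3. **SAE (8.3.2, 8.3.7.1).** On a plain reading of 8.3.1 the illness is an AE regardless of cause, and inpatient admission makes it serious. If 8.1.5 is read as taking infection out of the AE category, the SAE definition is not reached, because it starts from an AE or suspected adverse reaction. The two readings give opposite answers.
4. **AESI (Appendix A).** Infection itself is excluded, and this case has no listed concept.
5. **MAAE (8.3.9).** This covers hospital stays under 24 hours, emergency visits and unscheduled visits, and only if the event is considered related or possibly related. A longer admission does not fit the hospital-stay limb, and an infection judged unrelated fails the relatedness condition.
6. **New chronic condition (8.3.9).** This needs a condition expected to last at least 3 months with continuing care, so a short admission does not qualify.
7. **Collection of hospitalisations (8.2).** Data on admissions are collected. The same section says that safety endpoints come from AE reports, so collecting the admission does not by itself put it in the SAE endpoint.
8. **Exploratory endpoint (Table 4).** This holds sequence and serology results only.

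The result turns on step 3, and no sentence settles it.

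Elsewhere the protocol does settle the same kind of question. Section 8.3.10 says pregnancy is not an AE and then keeps any associated SAE reportable. Appendix A excludes infection from AESI reporting and then keeps listed complications reportable. Section 8.1.5 has no such second sentence.

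**The case against.** The strongest reply is that a route into the SAE data already exists. Section 8.1.5 says infection is not a *typical* AE, which is weaker than saying it is not an AE. The event it defines is a positive test, and an admission or death that follows can be seen as a separate occurrence under 8.3.1. Where the protocol excludes something it does so by name: infection from AESI reporting, and elective admissions from the SAE definition. No passage excludes infection from SAE reporting.

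This stands. A reader might infer that serious COVID-19 has been removed from the AE system and has no way into the SAE data. The text does not support that, because 8.3.1, 8.3.2 and 8.3.7.1 cover such a case on a plain reading. What the reply does not supply is a statement that those sections prevail over the more specific 8.1.5.

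The second reply is that the remaining gap is narrow. ARDS and respiratory failure, thromboembolism, cardiac injury, stroke and other complications are AESIs in all stages even when they occur during infection, and all AESIs go on an SAE form. This also stands. It leaves only serious cases without a listed concept.

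The third reply is that the case report forms or the manual of procedures may hold the instruction. They may, but they are not shown, and the conflict lies between current sections of the protocol itself.

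**Conclusion.** The point holds as an unresolved conflict between a specific rule and the general rules. Section 8.1.5 sends every confirmed infection to an exploratory assessment, while 8.3 makes one that leads to admission or death an SAE. Sites could therefore count SAEs differently. This should be corrected, but it does not undermine the trial.

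The size is limited in three ways.

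- **Cases.** Only serious infections without an Appendix A event are affected. A reader might want a count of lost SAEs. The protocol gives no COVID-19 admission rate. An assumed rate applied to all participants would only be an upper limit, because it would include cases already reported as AESIs and cases that sites report as SAEs anyway.
- **Comparison of arms.** Sites are asked to recruit for all arms within a stage (6.3.2), so different readings between sites would tend to be spread over the arms of a stage. The likelier effect is undercounting and inconsistency between sites and stages. Because the study is open label, uneven reporting by arm cannot be excluded, but nothing in the protocol shows that it would occur.
- **Disease enhancement.** A reader might also object that enhanced disease is named only in the stage 3 list of potential immune-mediated diseases. That is not part of this point. Section 2.2.1 ties special monitoring of those diseases to vaccines with adjuvant systems, which here means the AS03-adjuvanted stage 3 products. Severe respiratory complications are AESIs in every stage.

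The conclusion assumes that some sites would treat 8.1.5 as the governing rule because it is the one specific to COVID-19. The amendment history is not relied on.

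**What to change.** Reconcile 8.1.5 and Appendix A with 8.3.1 and 8.3.2. Add to 8.1.5 that a confirmed SARS-CoV-2 infection meeting any seriousness criterion in 8.3.2 is reported as an SAE in all stages, and that only non-serious infection is captured solely as an exploratory assessment. In Appendix A, next to the sentence keeping infection out of AESI reporting, add that this does not affect SAE reporting of serious cases.

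The change concerns the classification of data only. The halting criteria, the relatedness assessment and the AESI list stay as written. The cost is one sentence in each place, a note to sites and a few more SAE forms. If serious infections are already meant to be SAEs, the text only confirms it.
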